5.3.3. Other variable(s)

This section was modified with Amendment 3. For details, see Section [15.2](#).

The individual components of the primary efficacy and safety endpoint will be assessed as other endpoints.

The mean transaortic valve pressure gradient at approximately 360 days after randomization as measured by routine echocardiogram (TTE or TEE), if available, will be captured in the eCRF and it is considered as an exploratory study endpoint.

End of study

The end of the study as a whole will be reached as soon as the last visit of the last subject has been reached in all centers in all participating countries.

The primary completion event for this study occurs when the 440th subject experiences a positively adjudicated primary efficacy endpoint or earlier if the event rate is unexpectedly low. The efficacy cut-off date is defined as the date of the primary completion event.

For practical purposes, the anticipated efficacy cut-off date is set based on a projection of the date of the primary completion event before 400 subjects have experienced a positively adjudicated primary efficacy endpoint. When the anticipated efficacy cut-off date is set, on-site visit will be scheduled for all subjects within 6 weeks.

The primary completion date for this study according to the FDA Amendment Act is specified in a separate document (not part of this study protocol).

6. Study population

This section was modified with Amendment 3. For details, see Section 15.2.

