10.3.5. Analysis of the primary efficacy variable

This section was modified with Amendment 3. For details, see Section 15.2.

The analysis of the primary efficacy variable is performed on the Full Analysis Set (FAS). For superiority analysis the follow-up is censored at the last date of known outcome status or at the efficacy cut-off date, whichever comes first. Non-inferiority analysis is carried out under the OT data scope, i.e. follow-up is censored at two days after permanent discontinuation of the randomized treatment strategy. Censoring is assumed independent of the treatment group assignment.

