10.3.5.2. Testing for non-inferiority

This section was modified with Amendment 3. For details, see Section 15.2.

Using a log rank test adapted to non-inferiority testing the following (inferiority) null hypothesis (H_0) is tested at a one-sided significance level of 2.5%:

H_0 : $HR(t) \geq 1.2$ for all time points $t \geq 0$, (i.e. “the hazard for the primary efficacy endpoint in the rivaroxaban-based treatment group is more than 20% larger than that in the antiplatelet-based control group regarding”)

The one-sided alternative hypothesis (H_1) is:

H_1 : $HR(t) < 1.2$ for all time points $t \geq 0$, (i.e. “the hazard in the rivaroxaban-based treatment group for the primary efficacy endpoint is such that the HR is below 1.20”)

The following decision rule to test the null hypothesis of inferiority is applied:

If the upper boundary of 95% confidence interval (CI) for HR falls below 1.20, the null-hypothesis of inferiority (H_0) is rejected and non-inferiority of the rivaroxaban-based strategy (relative to the antiplatelet-based strategy) with regard to the primary efficacy endpoint can be claimed.

Hazard ratio and corresponding two-sided 95% confidence intervals are estimated based on a Cox proportional hazards model.

In order to preserve the type I error rate for efficacy testing, the two tests for the primary efficacy endpoint are technically placed in a hierarchical order, (1) testing for non-inferiority as described in this section followed by (2) testing for superiority as described in the previous section.

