10.4. Determination of sample size

This section was modified with Amendment 3. For details, see Section 15.2.

The sample size determination for the study was driven by requirements for testing superiority of the rivaroxaban-based strategy over the antiplatelet-based strategy as described above.

The expected 540 days event rate of the primary efficacy endpoint is 33.0% (5-7, 10). The target Relative Risk at 540 days is 0.80, i.e. a reduction of the 540 days event rate from 33.0% under antiplatelet-based regimen to 26.4% under the rivaroxaban-based regimen. Under the assumption of an exponential distribution, the hazard ratio equals 0.7654.

Under the above assumptions, with 360 days accrual period, and an 540 days median follow-up (minimum 360 days and maximum 720 days), randomization of 2 x 740 analyzable subjects is expected to yield 440 primary events (196 in the rivaroxaban-based treatment group and 244 in the antiplatelet-based control group). This provides 80% power at a 5% significance level, without interim analyses for efficacy.

The power calculation was based on a test using the Cox proportional hazards model and was performed with PASS version 12.0.6, with the module for two survival curves using Cox's proportional hazards model.

A sample size of sample size of 2 x 760 subjects allows for an attrition rate of 2.63%. The study is event driven and the number of randomized subjects is estimated to be required to collect 440 primary efficacy events. The study is planned to run until this number of events has been reached or to stop earlier if the event rate is unexpectedly low.

With this sample size, the study has > 90% power to show non-inferiority with a non-inferiority margin of 1.20 if the underlying hazard ratio ≤ 0.90 at a one-sided significance level of 2.5%. The non-inferiority margin of 1.20 was selected based on clinical appropriateness.

The final sample size will depend on multiple factors including the rate of accrual of the primary endpoint events. The Steering Committee of the trial will monitor the aggregate (blinded) event rate and may increase the sample size or duration of follow-up to achieve the planned target number of events in consultation with the sponsor.

Non-inferiority margin

The non-inferiority margin of 1.20 for the HR for the efficacy comparison as described in Section 10.3.5.2 was selected based on both clinical appropriateness and relevant studies in the area of TAVR.

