6.2.1.1 Testing for non-inferiority

Testing for superiority of the rivaroxaban-based strategy for the primary efficacy outcome is preceded by testing for non-inferiority, in the OT data scope, tested with the non-inferiority log rank test⁸.

Using an non-inferiority log rank test the following (inferiority) null hypothesis (H_0) is tested at a one-sided significance level of 2.5%:

$H_0: \widehat{HR}(t) \geq 1.20$ for all time points $t \geq 0$, (i.e. “the hazard for the primary efficacy endpoint in the rivaroxaban-based treatment group is more than 20% larger than that in the antiplatelet-based control group regarding”)

The one-sided alternative hypothesis (H_1) is:

Statistical Analysis Plan

Study No.: BAY59-7939-17938

Page: 17 of 31

$H_1: \widehat{HR}(t) < 1.20$ for all time points $t \geq 0$, (i.e. “the hazard in the rivaroxaban-based treatment group for the primary efficacy endpoint is such that the \widehat{HR} is below 1.20”)

The following decision rule to test the null hypothesis of inferiority is applied:

With the estimated drift parameter $\hat{q} = Z/V$ where Z is the LR statistic with its Variance V (note that $V \approx \text{events}/4$) and $\widehat{HR} = \exp(-\hat{q})$, the upper 97.5% limit of the confidence interval for \widehat{HR} is calculated as

$UL_{0.975}(\widehat{HR}) = \exp\left(-\left(\hat{q} - \frac{1.96}{\sqrt{V}}\right)\right)$ and will be compared with the NIM of 1.2. The null hypothesis $H_0: HR \geq 1.2$ will be rejected if $UL_{0.975}(\widehat{HR}) < 1.2$

If the null-hypothesis of inferiority (H_0) is rejected and non-inferiority of the rivaroxaban-based strategy (relative to the antiplatelet-based strategy) with regard to the primary efficacy endpoint can be claimed, proceed to section [6.2.1.2](#).

The following SAS code can be used to obtain the LR statistic:

```
ods output LogRankHomCov=work.LRHC HomStats=work.HomStats ;
proc lifetest data=work.infile alpha=0.025 method=km notable ;
time d2fDTE * DTE(0) ;
strata treat /test=(logrank) ;
run;

*from ODS datasets to needed variables, and calculations;
data work.logrank (drop=treat) ;
merge work.lrhc (where=(treat='0') keep=treat _0 rename=(_0=V)) 
      work.homstats (where=(treat='0') rename=(LogRank=Z) keep=LogRank
      treat) ;

q=Z/V;
HR=exp(-q);
UL=exp(-(q-(1.96/sqrt(V))));;
label
  Z="LR statistic"
  V="Variance of LR statistic"
  q="q"
  HR="HR"
  UL="Upper limit 0.975"
;
%put "on purpose no by statement for merge, 1 record per input dataset";
run;
/*

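### Protocol 10.4 states more than 90% non-inferiority power at a true HR of 0.90, but the 440 events at which the trial stops give about 85%

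*Protocol*

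**What the plan says.** Protocol section 10.4 sizes the trial for superiority and then adds that, with that sample size, "the study has > 90% power to show non-inferiority with a non-inferiority margin of 1.20 if the underlying hazard ratio" is no greater than "0.90 at a one-sided significance level of 2.5"%. The range includes 0.90 itself, so the claim has to hold there.

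The amount of information is fixed by events. Section 5.3.3 (End of study) says "The primary completion event for this study occurs when the 440th subject experiences a positively adjudicated primary efficacy endpoint". It also permits a sooner stop when events accrue far more slowly than planned. Section 10.4 says the same of the 440 events: "The study is planned to run until this number of events has been reached", again with the option of an earlier stop.

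Section 10.3.5.2 gives the test: the null hypothesis of inferiority "is tested at a one-sided significance level of 2.5"%, and it is rejected under this condition: "If the upper boundary of 95% confidence interval (CI) for HR falls below 1.20". On the data used, protocol section 10.3.5 states "Non-inferiority analysis is carried out under the OT data scope", and SAP section 6.2.1.1 agrees that superiority testing is "preceded by testing for non-inferiority, in the OT data scope". Neither document gives an expected number of on-treatment events or an on-treatment HR.

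**The concern.** An event count that gives 80% power to separate an HR of 0.7654 from 1 does not obviously give more than 90% power to separate 0.90 from 1.20. On the log scale the two distances are close: ln(1/0.7654) = 0.267 and ln(1.20/0.90) = 0.288. The non-inferiority power should therefore be only a little above the superiority power.

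The figure matters because section 10.3.5.2 allows non-inferiority to be claimed in its own right and makes it the gate to the superiority test. A reader judging the non-inferiority objective would take the risk of missing it at a true HR of 0.90 to be under 10%.

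**Working it through.** **Inputs.** From protocol 10.4: 440 events; design HR 0.7654; 33.0% and 26.4% event rates at 540 days; 360 days of accrual with 360 to 720 days of follow-up; 2 x 740 analyzable subjects from 2 x 760 randomized; margin 1.20; boundary HR 0.90; one-sided 2.5%. From protocol 7.1: 1:1 allocation.

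**Formula.** For a log-rank or Cox test with D events and 1:1 allocation (Schoenfeld approximation):

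Power = Φ( ln(margin/HR) × √D / 2 − 1.96 )

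For superiority the margin is 1. This matches the SAP 6.2.1.1 rule, which takes the variance of the log-rank statistic as about events/4.

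**Step 1: reproduce the plan's superiority figures.**
- HR = ln(1 − 0.264) / ln(1 − 0.330) = 0.7654, as stated.
- Events: 740 × (0.330 + 0.264) = 439.6, matching 440. Integrating over uniform accrual gives 437 (243 + 194), also close.
- Power: ln(1/0.7654) × √440 / 2 = 2.804; 2.804 − 1.960 = 0.844; Φ = 80.1%, matching the stated 80%.

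**Step 2: non-inferiority at HR 0.90 with 440 events.**
- ln(1.20/0.90) = 0.2877 and √440 = 20.976.
- 0.2877 × 20.976 / 2 = 3.017; 3.017 − 1.960 = 1.057; Φ = **85.5%**.
- The Freedman approximation gives 85.0%.
- Simulating the SAP decision rule (2 x 760, uniform 360-day accrual, exponential times, stop at the 440th event, 8,000 runs) gives 85.4%.

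**Step 3: what 90% would take.**
- Events at HR 0.90: 4 × (1.960 + 1.2816)² / 0.2877² = 508.
- True HR at 440 events: 1.20 × exp(−3.2415 × 2 / √440) = 0.881.

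**Step 4: power at 440 events by true HR.**

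| True HR | Power |
|---|---|
| 0.90 | 85.5% |
| 0.89 | 88.0% |
| 0.88 | 90.2% |
| 0.85 | 95.1% |
| 0.7654 | 99.7% |

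**Step 5: other readings at HR 0.90.**

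| Reading | Events | Power |
|---|---|---|
| 2 x 740 followed 360–720 days, no event stop | 465 | 87.3% |
| 2 x 760 followed 360–720 days, no attrition, no event stop | 478 | 88.2% |
| 440 events, one-sided 5% | 440 | 91.5% |

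Only the last exceeds 90%, and it contradicts the 2.5% given in protocol 10.3.5.2 and 10.4 and in SAP 6.2.1.1. The first two also ignore the event stop. At HR 0.90 the 440th event falls about 669 days (2 x 760) to 685 days (2 x 740) after the first randomization, before day 720. Reaching 508 events would take until about day 760 to 780.

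**Step 6: on-treatment data.** Censoring two days after permanent discontinuation can only remove events from the 440. The following counts are assumptions, since the documents give none. With an on-treatment HR of 0.90, 400 events give 82.0% and 350 give 76.8%. A more favourable on-treatment HR would offset the loss: 400 events at an HR of about 0.887 bring power back to roughly the 440-event value.

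**The case against.** The arithmetic is not seriously open to dispute. The case for leaving the sentence alone rests on its weight and on how firmly 440 caps the count.

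- **Little depends on it.** The trial is sized for superiority, non-inferiority is the preceding gate, and that gate has 99.7% power at the design HR. The sentence is true for every HR up to about 0.881, and the shortfall is 2.0 points at 0.89 and 4.5 points at 0.90. This stands, and it limits the consequence. It does not make the stated figure right, because the stated range includes 0.90.
- **The sentence refers to sample size, not events.** Read as subjects, the shortfall is about 2 to 3 points (88.2% or 87.3%). This is a fair alternative reading, but it still does not support more than 90%.
- **440 is a target, not a strict ceiling.** The operational cut-off is projected before 400 events, final visits follow within six weeks, and SAP 5.2.1 words the cut-off as the date when study treatments are discontinued. If the cut-off fell 42 days after the 440th event, the protocol's rates at HR 0.90 would give about 470 events and 87.7% before on-treatment losses. The SAP is indeed looser here. However, protocol 5.3.3 and 10.2.2 tie the cut-off to the 440th event, and the Steering Committee may extend follow-up or sample size only to reach the planned number. The overrun falls short of 90% too.
- **The on-treatment illustrations rest on invented counts.** Agreed. They show direction and sensitivity only, and the finding does not depend on them.

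**Conclusion.** The stated power is wrong as written. At a true HR of 0.90, margin 1.20 and one-sided 2.5%, the planned 440 events give 85.5%, which is 4.5 points below the stated lower bound. The chance of missing non-inferiority is then about 14.5%, not under 10%. No reading consistent with the documents reaches 90%: the range is 85.5% to 88.2%.

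The result assumes proportional hazards, 1:1 allocation and all 440 events being available to the test. The last assumption is favourable, because the test uses on-treatment data and the study may stop early. At 440 events the error affects only true HRs between about 0.88 and 0.90. The superiority sizing, margin, decision rule and type I error are untouched. A one-sided 5% input would produce a figure above 90%, but nothing in the documents confirms that this is the source.

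**What to change.** In protocol section 10.4, replace the non-inferiority power sentence with one to this effect: with 440 events in the non-inferiority analysis, power at one-sided 2.5% and margin 1.20 is about 85% for a true HR of 0.90 and 90% for a true HR of 0.88. Then state separately the number of on-treatment events assumed (expected to be below 440), the on-treatment HR assumed, and the power at those values.

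The cost is protocol wording and a slightly less favourable published figure. No change to the sample size, event target, margin or analysis is needed.

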10.5. Planned interim analyses

This section was modified with Amendment 3. For details, see Section 15.2.

No formal interim analysis is planned.

11. Data handling and quality assurance

11.1. Data recording

This section was modified with Amendment 3. For details, see Section 15.2.

The data collection tool for this study is a validated electronic data capture system called MARVIN (XClinical).

Data required according to this protocol are recorded by investigational site personnel via data entry into the internet based eCRF system, which Cardialysis (CRO) licenses from XClinical. MARVIN is validated by XClinical and Cardialysis for use in its clinical studies. MARVIN allows for the application of software logic to set-up data entry screens and data checks to ensure the completeness and accuracy of the data entered by the site personnel. Cardialysis extensively applies the logic to ensure data are complete and reflect the clinical data requirements of the study. Data queries resulting from the application of the software logic are resolved by the site personnel. The data are stored at a secure host facility maintained by XClinical and will be downloaded by Cardialysis each night. All access to the MARVIN system is through a password-protected security system that is part of the MARVIN software.

All internal Cardialysis, internal Mount Sinai (ARO), Bayer, and external investigator site personnel seeking access must go through a MARVIN training process before they are granted access to MARVIN for use in Bayer's clinical studies. Training records are maintained.

All personnel with access to the MARVIN system are supported by a Service Desk. The Service Desk is staffed with trained personnel to answer questions and ensure access is maintained such that data entry can proceed in a timely manner.

The MARVIN System contains a system-generated audit trail that captures any changes made to a data field, including who made the change, why the change was made, the date, and time it was made. This information is available both at the investigator's site and at Bayer. Data entries made in the MARVIN eCRF screens are supported by source documents maintained for all subjects enrolled in this study.

Source documentation

It is the expectation of the sponsor that key data entered into the eCRF has source documentation available at the site.

Study-specific data not needed for the subject's routine medical care (e.g. scores or questionnaires) may be entered directly into the eCRF, without availability of corresponding source documentation.

The site must implement processes to ensure availability of all required source documentation. A source document checklist (not part of this protocol) will be used at the site to identify the source data for key data points collected and the monitor will work with the site to complete this.

Data recorded from screening failures

Data of 'only screened subjects' will be recorded at least as source data, as far as the reason for the screening failure is identifiable. At minimum, the following data should be recorded in the eCRF:

- Demographic information (SID number; year of birth / age; sex; if applicable race / ethnicity)
- Date of IC
- Reason for failure of screening
- Date of last visit

If a subject is deemed a screening failure, all SAEs experienced during the screening period are documented and reported as described in Section [9.6.1.4](#) and [9.6.1.6](#).

11.2. Monitoring

This section was modified with Amendment 3. For details, see Section [15.2](#).

In accordance with applicable regulations, GCP, and sponsor's/CRO's/ARO's procedures, monitors will contact the site prior to the start of the study to review with the site staff the protocol, study requirements, and their responsibilities to satisfy regulatory, ethical, and sponsor's requirements. When reviewing data collection procedures, the discussion will also include identification and documentation of source data items.

The sponsor/designee will monitor the site activity to verify that the:

- Data are authentic, accurate, and complete
Supporting data may be requested (example: blood glucose readings to support a diagnosis of diabetes)

- Safety and rights of subjects are being protected
- Study is conducted in accordance with the currently approved protocol (including study treatment being used in accordance with the protocol)
- Any other study agreements, GCP, and all applicable regulatory requirements are met

The investigator and the head of the medical institution (where applicable) agrees to allow the monitor direct access to all relevant documents.

11.3. Data processing

Data will be collected as described in Section 11.1. Clinical data management will be performed in accordance with applicable sponsor's/CRO's standards and data cleaning procedures. This is applicable for data recorded on eCRF as well as for data from other sources (e.g. IxRS, laboratory, ECG, adjudication committees).

For data coding (e.g. AEs, medication), internationally recognized and accepted dictionaries will be used.

11.4. Missing data

Every effort will be undertaken to enhance completeness of data.

In time-to-event analysis subjects who have intentionally terminated follow-up will be censored at the time of the efficacy cut-off date. If loss-to-follow-up occurs, follow-up will be censored at the last date of known clinical outcome status.

Unless otherwise specified in the statistical analysis plan, no statistical techniques will be used to impute missing data for continuous or categorical variables. The number of subjects included in each analysis will be reported so that the reader can assess the potential impact of missing data.

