6.3. Withdrawal of subjects from study

All subjects will be encouraged to remain under observation for the full duration of the study. However, at any time during the study and without giving reasons, a subject may decline to participate further. The subject will not suffer any disadvantage as a result.

It is important though, to note that discontinuation of the assigned study treatment strategies is not equivalent to withdrawal of IC.

Moreover, withdrawal of IC does not mean withdraw of permission to collect further information. In whether this refers to permanent discontinuation or interruption of the assigned therapy (the most common expected scenario), unwillingness to attend on-site visits, unwillingness to have telephone contact, unwillingness to have any contact with study personnel, or unwillingness to allow contact with a third party (e.g. general practitioner) is to be assessed by the investigator. See Section [6.3.1.2](#) for detailed information on withdrawal of IC.

The reason for withdrawal (e.g. lost-to-follow-up, withdrawal of consent, protocol violation, AE, efficacy outcome reached, or subject unable/unwilling to comply with study medication, etc.) must be recorded in the eCRF and in the subject's medical records.

In all cases, every effort must be made to continue to follow the subject and survival status information must be determined for all randomized subjects by the end of the study.

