2. Withdrawal of consent and collection of vital status only allowed:

For subjects who withdraw consent for release of information, vital status only should be obtained. The measures taken for follow-up must be documented in the source data.

Vital status should be obtained when the anticipated efficacy cut-off date is set.

3. Withdrawal of consent and collection of further information not allowed:

In cases where subjects indicate they do not want to be contacted to collect vital status, the withdrawal of consent must be made separately as described under Section [13.3](#).

In this instance, all collected data so far remain in the study database.

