10.3.7. Analysis of the safety variables

This section was modified with Amendment 3. For details, see Section 15.2.

The analysis of the primary safety variable is performed on the Full Analysis Set (FAS) under the ITT data scope — that is, events are analyzed irrespective of their time of occurrence relative to termination of assigned study treatment strategy. Follow-up is censored at the last date of known outcome status or at the efficacy cut-off date, whichever comes first.

Kaplan-Meier estimates of cumulative risk and cumulative hazard functions for the primary safety variable are provided to evaluate the timing of event occurrence in the different treatment groups and the consistency of the respective treatment effects for all time points.

If the proportional hazards assumption holds for the primary safety variable, hazard ratio and corresponding two-sided 95% confidence intervals are estimated based on a Cox proportional hazards models.

On treatment analyses, pre-NOAF and post-NOAF analyses of the primary safety variable are performed as exploratory analyses.

All of the above analyses of the primary safety variable are descriptive, without formal statistical tests being performed.

The analyses of secondary safety variables are similar to those for secondary efficacy variables, without any sequential order.

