5.2 Data scopes

5.2.1 Data scopes according to intention-to-treat principle (ITT analysis)

Efficacy cut-off date

When the anticipated efficacy cut-off date is set, the sponsor informs each investigational site and all subjects must return to the clinic within 6 weeks in order to have a final assessment. This assessment will coincide with the EOT visit for the subjects under treatment. The efficacy cut-off date is the date when the study treatments are discontinued. This date will be determined by the Executive Committee (see protocol 5.3.3). From this day onwards subjects will be transitioned from the assigned strategy to an appropriate therapy, as per the clinical site standard of care.

Censoring of follow-up in ITT analysis

Censoring of follow-up for patients is on the efficacy cut-off date, or date of last known clinical status collected from Last Clinical Status form, or date of death (by CEC adjudication) whichever comes first.

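### Protocol 11.4, on its likelier reading, censors withdrawn subjects at the efficacy cut-off, while Protocol 10.3.5, 10.3.7 and SAP 5.2.1 use the earlier of last known status and cut-off: a minor conflict to settle in the SAP

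*Protocol*

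**What the plan says.** Protocol 11.4 gives two censoring rules for time-to-event analyses. The first is that "subjects who have intentionally terminated follow-up will be censored at the time of the efficacy cut-off date". The second reads: "If loss-to-follow-up occurs, follow-up will be censored at the last date of known clinical outcome status". The group in the first rule is not defined.

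The other places give one rule for all subjects, with no exception for withdrawal:

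- Protocol 10.3.5, primary efficacy: "For superiority analysis the follow-up is censored at the last date of known outcome status or at the efficacy cut-off date, whichever comes first".
- Protocol 10.3.7, primary safety: "Follow-up is censored at the last date of known outcome status or at the efficacy cut-off date, whichever comes first".
- SAP 5.2.1, ITT scope: "Censoring of follow-up for patients is on the efficacy cut-off date, or date of last known clinical status collected from Last Clinical Status form". It adds date of death and takes the earliest of the three. The death term does not affect a living subject who withdraws.

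Protocol 6.3.1.2 distinguishes three kinds of consent withdrawal. Subjects of the first kind are followed to the cut-off. For the second kind only survival is sought: "Vital status should be obtained when the anticipated efficacy cut-off date is set". For the third kind nothing more is collected: "In this instance, all collected data so far remain in the study database".

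Protocol 10.1 assigns further detail on censoring to the SAP. SAP 4.2 keeps dropouts in the analysis but gives no censoring date for them. SAP section 7 records no changes to the planned analysis. Neither document says which rule prevails.

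**The concern.** Three features of the text make withdrawal the likelier meaning of the first 11.4 rule. It stands under the heading on missing data. It is set against loss to follow-up. Protocol 6.3 also treats loss to follow-up and consent withdrawal as separate items: "The reason for withdrawal (e.g. lost-to-follow-up, withdrawal of consent, protocol violation".

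On that meaning, a subject who refuses all further data at day 90 stays in the risk set until the cut-off, although no event could be recorded. With the planned maximum follow-up this is up to 720 - 90 = 630 unobserved days counted as event-free.

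If withdrawal is equal in the two arms, the distortion largely cancels in the hazard ratio. If it is unequal, which is possible in an open-label trial, the arm with more withdrawal looks better than it is. At stake are the ITT superiority test and the other ITT comparisons. The primary bleeding comparison is descriptive, so there the effect would be only a slightly biased hazard ratio.

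**Working it through.** **Plan figures (Protocol 10.4).** The 540-day risks are 33.0% and 26.4%, follow-up is 360 to 720 days, and the plan has 2 x 740 analyzable subjects, 2 x 760 randomized, and 440 events for 80% power.

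- HR = ln(1 - 0.264) / ln(1 - 0.33) = 0.7654, as stated.
- Events (Schoenfeld) = 4 x (1.96 + 0.8416)² / (ln 0.7654)² = 439.2, rounded up to 440, as stated.
- Attrition = 1 - 740/760 = 2.63%, as stated, or 20 subjects per arm.

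These figures do not depend on the censoring rule.

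**Assumptions for the size.** The documents give no withdrawal rate beyond the 2.63% allowance. The upper case treats all of it as full withdrawal. A 2:1 split with mean 2.63% is 3.51% v 1.75%; a 3:1 split is 3.94% v 1.31%.

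**Simulation.** 2 x 760 subjects, exponential event times with 33% risk at 540 days, follow-up uniform on 360-720 days, exponential withdrawal unrelated to event risk, and a log-rank test at 1.96. There were 60,000 null trials per row (standard error about 0.07 percentage points). The error is that of the superiority test taken alone.

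| Full withdrawal by day 540, rivaroxaban / control | One-sided error, 11.4 rule | One-sided error, earlier-of-two-dates rule | Null HR, 11.4 rule |
|---|---|---|---|
| 2.63% / 2.63% | 2.48% | 2.51% | 1.000 |
| 3.51% / 1.75% | 3.18% | 2.45% | 0.990 |
| 3.94% / 1.31% | 3.46% | 2.36% | 0.985 |
| 1.75% / 3.51% | 1.80% | 2.39% | 1.010 |
| 1.31% / 3.94% | 1.73% | 2.53% | 1.015 |
| 1.75% / 0.88% (half the allowance) | 3.03% | 2.67% | 0.995 |
| 1.97% / 0.66% (half the allowance) | 2.92% | 2.43% | 0.993 |

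Independent repeats of rows two and three gave 3.2-3.3% and 3.6-3.7%. The shift comes from few unseen events: on average 4.2 v 2.1 at 2:1 and 4.7 v 1.6 at 3:1.

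Fixed follow-up yields about 492 events under the null, but the trial stops at 440. With stopping at 440 the errors are about 3.1% (2:1) and 3.5% (3:1). Hence the range 3.1-3.7%.

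**Hand check.** The shift in z is -ln(null HR) x √(events/4).

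- 2:1 with 492 events: 0.01005 x 11.09 = 0.111, so the error is 1 - Φ(1.849) = 3.2%.
- 3:1 with 492 events: 0.01511 x 11.09 = 0.168, so the error is 1 - Φ(1.792) = 3.7%.

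**Power at HR 0.7654** (40,000 trials, standard error 0.2 points), 11.4 rule v earlier-of-two-dates rule:

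- Balanced: 80.0% v 80.2%.
- 2:1 toward control: 77.1% v 80.1%.
- 3:1 toward control: 75.3% v 80.1%.

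**The case against.** The best reply is that the operative rule is already clear. Three sections state it without exception, Protocol 10.1 hands censoring to the SAP, and nothing in the SAP implements 11.4. Most of this stands, and it is why the point is minor. What it leaves open is precedence. Protocol 10.1 asks the SAP for more detail and does not let it override a protocol rule. The deference to the SAP within 11.4 is attached to imputation, not to the censoring sentence.

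There is also a reading without conflict. The protocol's usual terms are withdrawal of consent and discontinuation, not intentional termination. Protocol 9.4 collects events up to 30 days beyond the final visit, so a rule that cuts completers off at the cut-off date would have a purpose. The two 11.4 sentences would then be 10.3.5 in two halves. This cannot be excluded, but it fits poorly with the heading and with a sentence about subjects who themselves end follow-up. Even so, the wording would need correcting.

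The affected group is narrow, because only the third kind of withdrawal gives wholly unobserved time. That stands too.

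A reader might infer that the primary result will be biased toward rivaroxaban. The documents do not support this: they give no withdrawal rate by arm, and the direction could as well be the reverse. A reader might also assume heavier withdrawal. At 10% v 5% the error would be about 5% if withdrawals are spread over follow-up and about 9% if all fall in the first 90 days. Those rates are about two to four times the only attrition figure in the plan.

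**Conclusion.** The conflict is real on the likelier reading of 11.4, and it is minor. On that reading the 11.4 rule is wrong for subjects who refuse all further data. The rule in Protocol 10.3.5, 10.3.7 and SAP 5.2.1 is right and will probably be applied, in which case there is no effect.

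If 11.4 were applied, balanced withdrawal would leave the one-sided error at 2.5%. The figures of 3.1-3.7% for error and 75-77% for power are an illustrative upper case. They need three things at once: 11.4 overriding the SAP, the whole 2.63% allowance being full withdrawal, and a 2:1 or 3:1 split. With half the allowance the error is about 2.9-3.0%.

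The non-inferiority test is largely protected, because SAP 5.2.2 also stops follow-up at last known status or shortly after treatment is discontinued.

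The stronger conclusion, that the primary analysis is mis-specified, does not follow from the documents. Confidence is medium, because the intent of the 11.4 sentence cannot be settled from the text.

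**What to change.** Add to SAP 5.2.1: *This rule applies to all subjects, including those who withdraw from follow-up, and supersedes Protocol 11.4.*

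At the next protocol amendment, replace both 11.4 censoring sentences with: *Subjects who withdraw from follow-up or are lost to it are censored on the efficacy cut-off date or when outcome status was last known, whichever is earlier.*

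The SAP line is enough to resolve the conflict. It needs no new data, and the 440 events and 2 x 760 subjects are unchanged. An amendment needs investigator signatures and external approvals (Protocol 13.1.2), so the 11.4 wording is not worth an amendment of its own.

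The fix should not be extended to ignoring later deaths among subjects who allow vital status only. All-cause death is part of the primary endpoint, and the ITT scope in Protocol 10.2.2 takes in every outcome event observed up to the cut-off. Dropping those deaths would create a new conflict between protocol and SAP.
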